9.8.1. Total Blood Loss

Total loss will be calculated separately using two separate methods. The first method is based on Hct and the second method is based upon Hb. Total blood loss will be calculated at 6, 12, 24, 48, 72, 120 hours, and Day 7 postsurgery for each subject. Descriptive statistics summarizing the total blood loss will be summarized by postsurgical timepoint and treatment group for the efficacy analysis population for each method. Baseline is considered the last value measured before the surgery.

Total BV in mL will be calculated using the Nadler formula ([Nadler 1962](#)) at baseline by

$$BV_{baseline} = (a * h^3 + b * w + c)$$

where h = height (m), w = baseline weight (kg), $\{a=0.3669, b=0.03219, c=0.6041\}$ for males and $\{a=0.3561, b=0.03308, c=0.1833\}$ for females. The $BV_{baseline}$ is used in methods 1 and 2 to determine blood loss.

Method 1 ([Gibon 2013](#)):

Total RBC loss is in mL calculated by the following formula:

$$RBC_{lost} = BV_{baseline} * (Hct_{baseline} - Hct_{postop\ hour}) + BV_{transfused}$$

where $Hct_{baseline}$ is measured as the volume percentage of red blood cells in the blood at baseline, $Hct_{post-op\ hour}$ is measured as the volume percentage of red blood cells in the blood at the specified postsurgical timepoint in hours, total $BV_{baseline}$ is measured in mL, and $BV_{transfused}$ is the mL volume of blood transfused to the subject.

Method 2 ([Gao et al, 2015](#)):

Another method of calculating blood loss is presented by Gao as follows:

$$Hb_{loss} [g] = BV_{baseline} [\text{mL}] \cdot (Hb_{baseline} [\text{g/L}] - Hb_{postop} [\text{g/L}]) \cdot 0.001 [\text{L/mL}] + Hb_t [\text{g}],$$

$$Hb_t = BV_{transfused} [\text{Unit}] \cdot 52 [\text{g/Unit}], \text{ and}$$

$$RBC_{lost} [\text{mL}] = 1000 \times Hb_{loss} [\text{g}] / Hb_{baseline} [\text{g/L}],$$

where Hb_{loss} is the total loss of hemoglobin in gram, $BV_{baseline}$ is the presurgery blood volume in mL, $Hb_{baseline}$ and Hb_{postop} are the presurgery and post surgery hemoglobin concentration in g/L, Hb_t is the amount of hemoglobin transfused in gram, $BV_{transfused}$ is the banked blood transfused in Unit, and RBC_{lost} is the total volume of RBC lost. The above formulae can be simplified as

$$RBC_{lost} = \frac{BV_{baseline} * (Hb_{baseline} - Hb_{postop}) + BV_{transfused} * 52000}{Hb_{baseline}}.$$

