Total blood loss upon arrival at the PACU and at 6, 12, 24, 48, 72, 120 hours, and Day 7 will be summarized using descriptive statistics [n, mean, SD, minimum, median, and maximum] for method 1 and method 2 separately. When both methods are presented together on the same graph, method 1 will be represented using a solid line (line=1) and method 2 will be represented using a dashed line (line 2).

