		DDMONYYYYTHH:MM	120 hrs	xxx.x	xxx.x	xxxx.x	xxx.x
		DDMONYYYYTHH:MM	Day 7	xxx.x	xxx.x	xxxx.x	xxx.x

Note: Blood volume transfused is since the last Timepoint. Blood Volume is calculated according to section 9.8.1 of the Statistical Analysis Plan for study 404-C-201: For method 1, blood loss is in mL calculated by: $RBC_{lost} = BV_{baseline} * (Hct_{baseline} - Hct_{post-op\ hour}) + BV_{transfused}$

Source: list SAS datasets used to create listing
SAS X.Y

DDMONYYYYTHH:MM
program_name

Note to programmer: Sort by collection date and time. Timepoints outside of the schedule windows should be listed under "Scheduled Timepoint" as "Unscheduled". Do not split a subject's data across pages.

Pacira Pharmaceuticals
Listing 16.2-6.1.2: Calculated Blood Loss - Method 2 - Randomized Subjects
Randomized Treatment: TTTTTT

(Page X of Y)

Protocol: 404-C-201

Site	Subject	Date and Time	Timepoint	Blood Volume Transfused (g)	Hemoglobin (g/dL)	Calculated Blood Volume (mL)	Calculated Blood Loss (mL)
XXX	XXX-YYYY	DDMONYYYYTHH:MM	Baseline	xxx.x	xxx.x	xxxx.x	N/A
		DDMONYYYYTHH:MM	PACU	xxx.x	xxx.x	xxxx.x	xxx.x
		DDMONYYYYTHH:MM	6 hrs	xxx.x	xxx.x	xxxx.x	xxx.x
		DDMONYYYYTHH:MM	12 hrs	xxx.x	xxx.x	xxxx.x	xxx.x
		DDMONYYYYTHH:MM	24 hrs	xxx.x	xxx.x	xxxx.x	xxx.x
		DDMONYYYYTHH:MM	48 hrs	xxx.x	xxx.x	xxxx.x	xxx.x
		DDMONYYYYTHH:MM	72 hrs	xxx.x	xxx.x	xxxx.x	xxx.x
		DDMONYYYYTHH:MM	120 hrs	xxx.x	xxx.x	xxxx.x	xxx.x
		DDMONYYYYTHH:MM	Day 7	xxx.x	xxx.x	xxxx.x	xxx.x
		DDMONYYYYTHH:MM	Baseline	xxx.x	xxx.x	xxxx.x	N/A
XXX	XXX-YYYY	DDMONYYYYTHH:MM	PACU	xxx.x	xxx.x	xxxx.x	xxx.x
		DDMONYYYYTHH:MM	6 hrs	xxx.x	xxx.x	xxxx.x	xxx.x
		DDMONYYYYTHH:MM	12 hrs	xxx.x	xxx.x	xxxx.x	xxx.x
		DDMONYYYYTHH:MM	24 hrs	xxx.x	xxx.x	xxxx.x	xxx.x
		DDMONYYYYTHH:MM	48 hrs	xxx.x	xxx.x	xxxx.x	xxx.x
		DDMONYYYYTHH:MM	72 hrs	xxx.x	xxx.x	xxxx.x	xxx.x
		DDMONYYYYTHH:MM	120 hrs	xxx.x	xxx.x	xxxx.x	xxx.x
		DDMONYYYYTHH:MM	Day 7	xxx.x	xxx.x	xxxx.x	xxx.x

Blood volume transfused is since the last Timepoint. Blood Volume is calculated according to section 9.8.1 of the Statistical Analysis Plan for study 404-C-201: For method 2, blood loss is in mL calculated by:

$$RBC_{lost} = \frac{1000 * (BV_{baseline} * (Hb_{baseline} - Hb_{post-op\ hour})) * 0.001 + 52 * BV_{transfused}}{Hb_{baseline}}$$

Source: list SAS datasets used to create listing
SAS X.Y

DDMONYYYYTHH:MM
program_name

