15. TABLE OF CONTENTS FOR FIGURES

Figure 14.2-9.1: Plot of Total Blood Loss over Time by Treatment (Method 1 Hct) - Efficacy Analysis Set	105
Figure 14.2-9.2: Plot of Total Blood Loss over Time by Treatment (Method 2 Hb) - Efficacy Analysis Set	106
Figure 14.2-9.3: Plot of Total Blood Loss over Time by Treatment (Both Methods) - Efficacy Analysis Set	107
Figure 14.4-3.1: Plot of Mean (\pm SE) TXA Concentration (ng/mL) over Time by Treatment - PK Analysis Set	108
Figure 14.4-3.2: Plot of ln Mean (\pm SE) TXA Concentration (ng/mL) over Time by Treatment - PK Analysis Set	109
Figure 14.4-3.3: Plot of Individual Subject TXA Concentrations (ng/mL) over Time - PK Analysis Set	110
Figure 14.4-3.4: Plot of Mean TXA 24h AUC vs 24h Blood Loss by Method - PK Analysis Set	113

Pacira Pharmaceuticals
Figure 14.2-9.1: Plot of Total Blood Loss over Time by Treatment (Method 1 Hct) - Efficacy Analysis Set

Source: list SAS datasets used to create listing
SAS X.Y

DDMONYYYYTHH:MM
program_name

Note to programmer: Margins on the y-axis should be adjusted, but consistent for figures 14.2-9.1, 14.2-9.2, and 14.2-9.3. Use template Figure 14.2-9.1 for the following Figure:

[figure not shown]
Figure 14.2-9.2: Plot of Total Blood Loss over Time by Treatment (Method 2 Hb) - Efficacy Analysis Set

Pacira Pharmaceuticals

(Page X of Y)

Protocol: 404-C-201

Figure 14.2-9.3: Plot of Total Blood Loss over Time by Treatment (Both Methods) - Efficacy Analysis Set

Source: list SAS datasets used to create listing
SAS X.Y

[figure not shown]
DDMONYYYYTHH:MM
program_name

Pacira Pharmaceuticals

(Page X of Y)

Protocol: 404-C-201

Figure 14.4-3.1: Plot of Mean (\pm SE) TXA Concentration (ng/mL) over Time by Treatment - PK Analysis Set

[figure not shown]

Source: list SAS datasets used to create listing
SAS X.Y

DDMONYYYYTHH:MM
program_name

Pacira Pharmaceuticals (Page X of Y)
Figure 14.4-3.2: Plot of ln Mean (\pm SE) TXA Concentration (ng/mL) over Time by Treatment (for Subjects Enrolled After Protocol Amendment 2) - PK Analysis Set

Protocol: 404-C-201

Source: list SAS datasets used to create listing

DDMONYYYYTHH:MM

SAS X.Y
Pacira Pharmaceuticals

[figure not shown]
[figure not shown]
(Page X of Y)

program_name
Protocol: 404-C-201

Figure 14.4-3.3: Plot of Individual Subject TXA Concentrations (ng/mL) over Time - PK Analysis Set

[figure not shown]
[figure not shown]
Subject [contact] DepoTXA 400

[figure not shown]
Subject [contact] DepoTXA 400

Subject [contact] DepoTXA 800

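### SAP 9.8.1: blood volume comes out in litres but is declared mL, and a red-cell volume (Method 1) and a whole-blood volume (Method 2) are both reported and overlaid as total blood loss

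*SAP*

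**What the plan says.** Section 9.8.1 states: "Total BV in mL will be calculated using the Nadler formula". Height is in metres, weight in kilograms, and the printed formula carries no factor of 1000. The result feeds both methods.

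- **Method 1** is introduced with "Total RBC loss is in mL calculated by the following formula". It multiplies baseline blood volume by the fall in haematocrit (Hct) and adds a transfusion term, which "is the mL volume of blood transfused to the subject". Hct is defined as a volume percentage.
- **Method 2** converts the fall in haemoglobin (Hb) to grams, adds 52 g per transfused unit, and divides by baseline Hb concentration. The result, the SAP says, "is the total volume of RBC lost".

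The outputs do not keep these names. Section 9.8.1 summarises both results as total blood loss. The footnote of Listing 16.2-6.1.1 gives the Method 1 expression under "For method 1, blood loss is in mL calculated by". Section 15 plans "Plot of Total Blood Loss over Time by Treatment (Method 1 Hct) - Efficacy Analysis Set" and, for Figure 14.2-9.3, "Plot of Total Blood Loss over Time by Treatment (Both Methods) - Efficacy Analysis Set". The overlay is deliberate: "When both methods are presented together on the same graph, method 1 will be represented using a solid line", with Method 2 dashed. Figure 14.4-3.4 plots 24-hour exposure against 24-hour blood loss by method.

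**The concern.** The printed formula does not give its declared unit, and the transfusion terms are already on the mL scale. The missing factor therefore cannot be treated as a harmless rescaling of the whole result.

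More lastingly, two different physical quantities share one name and one graph. A reader of Figure 14.2-9.3 would take the gap between solid and dashed lines as disagreement between two estimates of blood loss, when it arises by definition. Anyone taking Method 1 as an absolute blood loss for later planning would start from a figure less than half the intended quantity in untransfused subjects.

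In transfused subjects Method 1 is neither red-cell loss nor blood loss, so the relation between the methods depends on who was transfused.

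**Working it through.** The SAP gives no computed blood-loss figure to reproduce, so the check evaluates its formulas and units.

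**Inputs from 9.8.1.** Male coefficients 0.3669, 0.03219, 0.6041; female 0.3561, 0.03308, 0.1833; 52 g Hb per transfused unit.

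**Assumed inputs (not in the SAP).** Male, 1.75 m, 90 kg; Hct falling from 0.40 to 0.30; Hb from 133.3 to 100 g/L, i.e. Hct = 0.003 × Hb; a transfused unit of 300 mL (range 250 to 350 mL).

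**1. Unit of blood volume (BV).** BV = a·h³ + b·w + c.
- Male 1.75 m, 90 kg: 0.3669 × 5.359 + 0.03219 × 90 + 0.6041 = 5.468
- Female 1.50 m, 50 kg: 3.04
- Male 1.90 m, 135 kg: 7.47

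The SAP's own figures show these are litres. Read as mL, the first man's total Hb would be 5.468 × 133.3 × 0.001 = 0.73 g, against 52 g in one transfused unit. With × 1000 it is 729 g. If 5.468 were used as mL, the Hb-fall term of Method 2 would be 5.468 × 0.25 = 1.4 mL, against 52,000/133.3 = 390 mL per transfused unit.

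Entering Hct in percent does not rescue Method 1. With BV as printed it gives 5.468 × 10 = 54.7; with BV in mL it gives 54,680. Only BV in mL with Hct as a fraction works.

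**2. What each method measures (units corrected, no transfusion).**
- Method 1 = 5,468 × (0.40 − 0.30) = 547 mL. Volume times a red-cell fraction is red-cell volume.
- Method 2 = 5,468 × 33.3/133.3 = 1,367 mL. Grams of Hb divided by grams per litre of blood is whole-blood volume, whatever its label.
- Ratio = 547/1,367 = 0.40 = baseline Hct.

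Whenever Hb and Hct fall in proportion, the ratio equals baseline Hct. For baseline Hct of 0.36 to 0.48 and the same 0.10 fall, Method 2 is 547/0.36 = 1,519 mL down to 547/0.48 = 1,139 mL.

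**3. Transfusion term.** Red cells per unit consistent with 52 g Hb: 52,000 × 0.003 = 156 mL (146 to 166 mL for factors of 0.0028 to 0.0032). Excess per unit in Method 1, as a red-cell volume: 300 − 156 = 144 mL (from 250 − 166 = 84 to 350 − 146 = 204).

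| One unit transfused | mL | Ratio to Method 2 |
|---|---|---|
| Method 1 as written, 547 + 300 | 847 | 0.48 (0.45 to 0.51 for 250 to 350 mL units) |
| Method 1, red-cell term, 547 + 156 | 703 | 0.40 |
| Method 2, 1,367 + 390 | 1,757 | |

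A red-cell transfusion term restores the ratio; the printed term does not.

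**4. Effect on an arm difference.** If 3 of 15 subjects in one arm and none in another receive one unit, Method 1 shifts by 3/15 × 144 = 29 mL (17 to 41 mL), or 3.1 to 7.5% of 547 mL. With one extra transfused subject it is 144/15 = 9.6 mL; with equal transfusion it is zero.

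**The case against.** The intended scale of blood volume is plain. The SAP repeatedly calls it mL, Method 2 carries explicit units, Table 14.1-3.1 reports mL, and the listings format it in thousands. A value of 5.47 would be noticed at first output. This stands: the missing factor is an erratum, and the 1.4 mL result is unlikely ever to be reported. It does not touch the other two errors, whose results look plausible and would raise no flag.

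Section 9.8.1 also names Method 1 correctly as red-cell loss when nothing is transfused. True; the fault there lies in the Method 2 label, the output titles and the transfusion term.

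Dividing by baseline Hct is only one convention. At the mean Hct of 0.35, 547 mL of red cells corresponds to 547/0.35 = about 1,560 mL of blood. That also stands, but Method 2 uses the baseline convention, so it is the one that puts the methods on a common scale. Either way Method 1 is not a blood volume.

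The size of the transfusion error is assumed. Listing 16.2-6.2 shows units, not mL, and the SAP states no conversion. The arm shift depends entirely on transfusion imbalance and may be zero. Subject-level values could be recomputed from the variables in Listing 16.2-6.1.1, although reported group summaries could not be repaired by dividing by Hct.

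Finally, 9.8 plans no hypothesis test, pharmacokinetics is the primary objective, and arm comparisons within one method without transfusion stay on one scale. These points limit the severity; none makes the formulas or labels right.

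**Conclusion.** The concern holds and should be fixed. The litres error, a factor of 1000, follows from the SAP's own units and its 52 g per unit. The difference in kind between the methods follows from their algebra. Its size in untransfused subjects is baseline Hct (0.36 to 0.48 over the assumed range), provided Hb and Hct fall in proportion; read as total blood loss, Method 1 is then too low by that factor. The excess of 84 to 204 mL per transfused unit rests on assumed unit volumes and red-cell content. The damage is to descriptive tables, listings and figures for the first-listed efficacy endpoint, including the exposure plot. No error rate or power is affected.

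**What to change.** In 9.8.1:

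1. Multiply the Nadler result by 1000 and state that Hct enters as a fraction.
2. Choose one treatment of Method 1. Either keep it as red-cell loss, with a red-cell transfusion term, in its own table and figure and not overlaid with Method 2; or report [BV × (Hct_base − Hct_post) + transfused red-cell volume] / Hct_base as total blood loss, accepting that it will nearly coincide with Method 2.
3. In either case state the red-cell volume per transfused unit as an assumption consistent with 52 g Hb (about 156 mL if Hct = 0.003 × Hb in g/L; 146 to 166 mL for 0.0028 to 0.0032).
4. Relabel the Method 2 result as total blood loss.
5. Carry the formulas and names into the listing footnotes, Figures 14.2-9.1, 14.2-9.3 and 14.4-3.4, and Table 14.2-1.1, whose title now refers to blood volume rather than loss.

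As clarifications, align Listing 16.2-6.1.2 with 9.8.1 (Hb in g/L rather than g/dL; transfusion in units or as grams of Hb). Also state that the transfusion term is cumulative from baseline, since both calculated blood-loss listings show the amount since the previous timepoint.

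The cost is SAP wording and programming; no new data are needed.

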9.8.2. Incidence of transfusion

The incidence of transfusion (number of units/subject and number of subjects transfused) will be tabulated by postsurgical timepoint and treatment group for the efficacy analysis population with number and percentage of subjects. Percentages will be based on the number of subjects in the treatment group within the efficacy population.

9.8.3. Time to 90° Passive and Active Knee Flexion

The proportion of subjects capable of 90° passive and active knee flexion, separately, at 24, 48, and 72 hours will be tabulated with the number and percentage of subjects by postsurgical timepoint and treatment group for the efficacy analysis population. For patients enrolled after on/after Protocol Amendment 2, the summary table will be broken down by time of the day (AM or PM) of the assessment. The time to 90° knee flexion, for both passive and active separately, will be summarized using Kaplan-Meier estimates (n, 25th percentile, median, and 75th percentile). The actual time of assessment will be used for this calculation.

9.8.4. Time to Complete TUG Test

The time (seconds) to complete TUG test on study day 1 (postsurgical day 0), twice a day on study day 2 (6:00am - 10:00 am and 6:00pm - 10:00pm), at hospital discharge, and on study day 7 will be summarized by postsurgical timepoint and treatment group for the efficacy analysis population using descriptive statistics (n, mean, SD, minimum, median, and maximum). In addition, the amount of physical assistance required to complete the TUG test at each time point will be tabulated with the number and percentage of subjects in each category.

9.8.5. NRS Pain Scores

The NRS pain scores will be summarized using descriptive statistics (n, mean, SD, minimum, median, and maximum) at each scheduled timepoint. In addition, the AUC from the time a subject is admitted to the PACU through 72 hours will be calculated and summarized by treatment group for the efficacy analysis population using descriptive statistics (n, mean, SD, minimum, median, and maximum).

9.8.6. Change in Knee and Thigh Circumferences

Prior to Protocol Amendment 2, knee and thigh circumferences were collected for both surgical and non-surgical legs. Protocol Amendment 2 requires the collection only for the surgical leg. As such, for subjects enrolled prior to Amendment 2, the circumferences for the surgical and non surgical legs, the differences between the two, and their changes from baseline within subject will be summarized separately for the knee and thigh by treatment group for the efficacy analysis population using descriptive statistics (n, mean, SD, minimum, median, and maximum) for postsurgical day 2 (study day 3) and study day 7. For subjects enrolled after Amendment 2, only the circumferences of the surgical legs and their changes from baseline will be summarized.

9.8.7. Days to First Independent Ambulation

The number of days until the first independent ambulation will be summarized using Kaplan-Meier estimates (n, 25th percentile, median, and 75th percentile).

9.8.8. Surgical Wound Aspect Score (SWAS)

The SWAS will be tabulated by treatment group for the efficacy analysis population with number and percentage of subjects for the score of wound oozing, erythema, ecchymosis, and blisters for postsurgical day 2 (study day 3) and study day 7. In addition, the sum of the wound oozing, erythema, ecchymosis, and blister scores will also be tabulated by treatment group for the efficacy analysis population for postsurgical day 2 (study day 3) and study day 7. Percentages will be based on the number of subjects in the treatment group within the efficacy population.

9.9. Safety Analyses

The following safety assessments will be summarized:

- 12-lead ECGs at day 1 Preop (D1 Preop), and 1 hour and 12 hours after study drug administration.
- Vital signs (resting heart rate and blood pressure) at Baseline, and 5min, 15min, 30min, 1hr, 2hr, 4hr, 6hr, 8hr, 12hr, 16hr, 24hr, 36hr, 48hr, 60hr, 72hr, and 96hr after study drug administration.
- Neurological assessment at D1 Preop and at 12, 24, 36, 48, 60, 72, and 96 hours after study drug administration.
- Clinical laboratory testing (hematology [including fibrinogen and fibrin split products, lipid profile] and chemistry) at D1 Preop, at 48 hours, and at day 7.
- Creatinine clearance measurement at 48 hours and at day 7.
- Reoperations due to hematoma or wound dehiscence.
- Adverse events through study day 60.

No inferential statistics are planned for any of the safety assessments.

9.9.1. Electrocardiograms

Investigators will classify ECG tracings as ‘normal’, ‘abnormal not clinically significant’ or ‘abnormal clinically significant’. The investigator classifications will be tabulated by treatment and overall treatments at any time during the study and each assessment timepoint. A shift table comparing the investigator classification of the ECG results at baseline to each scheduled timepoint will also be provided.

9.9.2. Vital Signs

Vitals signs are resting heart rate (bpm), systolic blood pressure (mmHg), and diastolic blood pressure (mmHg). Vital signs will be summarized by treatment group at each assessment timepoint. Summaries will present both actual and change-from-baseline results. Baseline statistics will be presented at each assessment timepoint for those subjects reporting data at that timepoint.

9.9.3. Neurological Assessments

The neurological assessments summary will include the proportion of subjects who are oriented, and proportion of subjects who have any of the neurologic events (answered “Yes” to any of the additional questions regarding numbness, taste, hearing, vision, or twitching). Percentages will be based on the number of subjects in the treatment group. The number and percentage of subjects will be tabulated by treatment group at each assessment timepoint.

9.9.4. Clinical Laboratory Assessments

Clinical laboratory assessments are collected at D1 Preop and at 48 hours after study drug administration. Laboratory results will be summarized by treatment group at each assessment timepoint. Summaries will present both actual results and change from baseline results for each clinical laboratory parameter. Baseline statistics will also be presented for each clinical laboratory parameter.

Tabulations of the number and percentage of subjects with values outside the normal range will be provided by treatment group at baseline 48 hours, and day 7 for each parameter.

Shifts in laboratory results categorized as low (below the lower limit of the normal range), normal (within the normal range, limits inclusive) and above (above the upper limit of the normal range) will be presented in shift tables with baseline categories across the columns and 48 hour categories for the rows. Each treatment group separately and all DepoTXA subjects, in the safety analysis set, will be presented. Each cell will present the number and percentage of subjects in that cell. Due to the width of these tables, only one treatment will be presented per page.

Creatine clearance will be summarized for study day 7 in a similar manner as the other laboratory parameters at 48 hours.

9.9.5. Reoperation Due to Hematoma or Wound Dehiscence

The number and percentage of subjects with reoperations due to hematoma or wound dehiscence will be tabulated by treatment group and for All DepoTXA.

9.9.6. Adverse Events

Adverse events will be coded using MedDRA version 19.1 or higher.

A TEAE will be any adverse event with the onset date and time on or after the start date and time of study drug administration and within 30 days of the dose, or a pre-existing medical condition that worsens in intensity after the start of study drug (date and time) and within 30 days of the dose.

If an AE has a partial onset date and time the imputed start and stop dates and times will be used to determine treatment-emergence (e.g., stop date and time is before start date and time of study

treatment). All AE summaries will present TEAEs only; AEs that are not treatment-emergent will be included in listings but not summarized.

The incidence of subjects reporting TEAEs will be tabulated by the number and percentage of subjects reporting the TEAE. Incidence is defined as a subject reporting at least one TEAE within the summary level. Summary levels are 'at least one TEAE', system organ class and preferred term. Subjects will be counted only once within each reporting level on the table. For example if a subject reports a TEAE of headache on two separate occasions, the subject will be counted only once in the headache row of the table. Similarly if a subject reports two separate TEAEs within the same system organ class the subject will only be counted once in the summary row for that system organ class. A summary of subjects reporting at least one TEAE during the study will also be presented.

The first row on every TEAE table will be the number and percentage of subjects reporting at least one TEAE. Subsequent rows will be presented in descending order of subject counts for the overall treatment group with the most common system organ class first, followed within each system organ class by the preferred terms in descending subject count order. For tables presenting the severity or relation to study treatment of TEAE, the sort order will be determined by the number and percentage of subjects reporting the preferred term, thus the sort order of rows will remain the same for the relation or severity tables as the tables by preferred term.

The following summaries will be presented for the TEAEs reported by the subjects:

An overview of all TEAEs, serious TEAEs and TEAEs of Special Interest will present the number and percentage of subjects in the following categories:

- Any TEAE
 - Maximum severity: Mild
 - Maximum severity: Moderate
 - Maximum severity: Severe
- At least one related TEAE
- At least one serious TEAE
- At least one related serious TEAE
- Subjects discontinued because of a TEAE
- Died during the study

Subjects will be counted once in each of the above categories except for maximum severity. Subjects will be counted only once at the highest severity reported. For example, if a subject has a mild and severe headache and a moderate rash, the subject will be counted under maximum severity of severe only.

Adverse event tables will present the data by treatment group and across all treatment groups. Incidence tables will be created for the following groups of TEAEs:

- All TEAEs
- Study treatment-related TEAEs
- TEAEs leading to study withdrawal
- Study treatment-related TEAEs leading to study withdrawal
- All TEAEs by severity
- All TEAEs by relationship to study treatment

- All Serious TEAEs
- All Nonserious TEAEs (CT.gov only)
- Study treatment-related serious TEAEs
- Serious TEAEs leading to study withdrawal
- Study treatment-related serious TEAEs leading to study withdrawal
- Serious TEAEs resulting in death
- Study treatment-related serious TEAEs resulting in death
- All TEAEs of special interest
- Study treatment-related TEAEs of special interest
- TEAEs of special interest leading to study withdrawal
- Study treatment-related TEAEs of special interest leading to study withdrawal
- TEAEs of special interest resulting in death
- Study treatment-related TEAEs of special interest resulting in death

If there are no AEs to report on any of the above tables, the table should be created with the line ‘no adverse events were reported’ in the body of the table.

Adverse events will be considered related if the investigator assessment of relationship to study treatment is either ‘possible’, ‘probable’ or ‘definite’ or if no investigator assessment is provided.

Treatment emergent AESIs include changes in color vision, venous thromboembolism or pulmonary embolism, and oliguria.

A listing of the mapping of the SOC and PTs to verbatim terms will be presented.

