7. DEFINITIONS

Study Day

Study Day 1 is defined as the day of surgery. Study day is calculated as the date of event minus the date of surgery plus one (1), if the date of event is on or after the date of surgery. Study day is based on the calendar dates, thus days before the date of study drug administration have negative values while those on or after the date of surgery have positive values.

Treatment-emergent Adverse Events

A TEAE will be any adverse event or pre-existing medical condition that worsens in intensity after the start of study drug and within 30 days of the last dose.

Time 0 (zero)

Time 0 is defined as the date and time of the start of study drug administration.

Time Periods

All schedule times have a window associated with them (see Time and Events Schedule in the Protocol for individual timepoint windows). Various time frames that are dependent on these windows are used in the data analyses. Table 1 defines the actual elapsed times with allowance for the windows that can be included in the window.

Table 1: Time Periods

Defined time frame	Acceptable elapsed times
5 min	3-7 min
15 min	12-18 min
30 min	25-35 min
1h	50-70 min
2h	105-135 min
4h	225-255 min
6h	345-375 min
8h	450-510 min
12h	690-750 min
16h	15-17h
24h	23-25h
36h	34-38h
48h	46-50h
60h	57-63h
72h	68-76h
96h	90-102h
120h	114-126h
Study Day 7	Study Day 6-8
Study Day 14	Study Day 13-15
Study Day 30 Call	Study Day 27-33
Study Day 60 Call	Study Day 57-63

If there are two or more data points that fit the time window the data point that occurs the closest, in absolute value, to the scheduled observation will be used.

Baseline

Baseline is defined as the last available measurement or assessment prior to the start of study drug administration.

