9.1.1.2. Adverse Event Date or Time

It is expected that all necessary information on adverse events and the surgeries (start and stop date and time) will be complete. Unless an adverse event can be excluded as a treatment emergent by the known start and stop date/time, the adverse event should be considered treatment emergent.

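### Section 9.9 promises adverse event summaries through Study Day 60, but the 30-day TEAE limit keeps dated events with onset from Day 32 out of every AE incidence table

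*SAP*

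**What the plan says.** Section 9.9 opens with a list of safety assessments that it says will be summarized. The last item is "Adverse events through study day 60".

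Section 7 restricts a TEAE to an event or worsening "after the start of study drug and within 30 days of the last dose". Section 9.9.6 repeats the 30-day limit, worked in date and time from the dose, and then states: "All AE summaries will present TEAEs only; AEs that are not treatment-emergent will be included in listings but not summarized".

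The incidence tables listed in Section 9.9.6 are all groups of TEAEs, including the serious, special-interest and fatal-event tables. The table titles in Section 13 agree. On events of special interest the text reads: "Treatment emergent AESIs include changes in color vision, venous thromboembolism or pulmonary embolism, and oliguria".

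Table 1 in Section 7 gives the Day 60 call a window of "Study Day 57-63". The all-AE and all-SAE listings (16.2-11.1 and 16.2-11.3) are not limited to TEAEs.

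**The concern.** Follow-up runs to the Day 60 call, and Section 9.9 says the adverse events of that whole period will be summarized. Section 9.9.6 stops tabulation at 30 days after the dose. A programmer who follows Section 9.9.6 does not deliver what Section 9.9 promises.

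Two consequences matter.

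- **Special-interest events.** VTE/PE is a pre-declared event of special interest. If the only such event were a fully dated PE on Day 40, the special-interest table would be empty. Section 9.9.6 then applies: "If there are no AEs to report on any of the above tables, the table should be created with the line", followed by wording that none were reported. The listing would show the PE.
- **Deaths.** The overview row "Died during the study" is not worded as limited to TEAEs, whereas the fatal-event tables are. A death from an event that itself began after Day 31 could be counted in the overview while the fatal-event table is empty.

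**Working it through.** The SAP states no figure to reproduce. The check is date arithmetic under its own rules, followed by a search for any output that counts a late event.

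**Inputs**
- Section 7: the day of surgery is Study Day 1; study day = event date − surgery date + 1.
- Sections 7 and 9.9.6: the TEAE window is 30 days from the dose. There is one dose, given on Day 1.
- Section 9.9: summaries through Study Day 60.
- Section 7, Table 1: the Day 60 call falls on Study Day 57 to 63.
- Section 6: about 60 subjects, 15 per group.

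**Last TEAE day.** Dose date + 30 days gives 30 + 1 = Study Day 31. Because Section 9.9.6 works in date and time, the window closes partway through Day 31. An onset on Day 32 is outside it in any case.

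**Days excluded from the AE incidence tables**

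| End of follow-up | Days excluded | Share of days |
|---|---|---|
| Day 57 | 57 − 31 = 26 | 26/57 = 46% |
| Day 60 | 60 − 31 = 29 | 29/60 = 48% |
| Day 63 | 63 − 31 = 32 | 32/63 = 51% |

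**Share of events excluded.** The SAP gives no onset timing, so this rests on assumption. With exponential onset of mean *m* days, the share of events by Day 60 that start after Day 31 is (e^(−31/m) − e^(−60/m)) / (1 − e^(−60/m)).
- m = 10: (e^−3.1 − e^−6.0)/(1 − e^−6.0) = 4.3%
- m = 20: (e^−1.55 − e^−3.0)/(1 − e^−3.0) = 17.1%
- Uniform onset: 29/60 = 48%

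**One event, as illustration.** A single dated PE on Day 40 is 1/15 = 6.7% of its group and 1/60 = 1.7% overall. The special-interest table would show 0 for it.

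**Where late events still appear**
- Listings 16.2-11.1 and 16.2-11.3 include them, with a TEAE flag.
- Under Section 9.1.1.2, if known dates cannot exclude an event, "the adverse event should be considered treatment emergent". The gap is therefore confined to events with a known late onset.
- The overview death row may count late deaths, and Table 14.1-1 counts death and adverse event as reasons for discontinuation. Neither gives an event term.
- Table 14.3-7 counts reoperations for hematoma or wound dehiscence.

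None of these is a by-group table of late adverse events, serious events or special-interest events by preferred term.

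**The case against.** The best counter-argument is that Section 9.9 is an overview. Its other bullets mostly give collection times, so the Day 60 item may only describe the observation period, with Section 9.9.6 as the operative and more specific text. Taken literally, the bullet has no start date and would also pull in events between consent and dosing. On this view a programmer knows what to produce, and one clause in Section 9.9 would remove the conflict.

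Further points on that side:
- A 30-day TEAE window with other events listed is an openly stated choice in a single-dose study without safety inference.
- The listings are arranged by treatment, and with about 15 subjects per group a late PE can be read from them.
- An empty table titled as TEAEs of special interest would be true for TEAEs.
- The overview death row sits under a heading about TEAEs and may itself be limited to them. A death after Day 31 from an event that began earlier would still be in the fatal-event table.

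Much of this stands. The window is acceptable, no data are lost, and the death mismatch is only possible: it needs a fatal event with onset after Day 31 and an overview row read without the TEAE limit. The collection-period reading does not hold as the text is written, because the lead-in says the listed items will be summarized. Rewording Section 9.9 alone would remove the contradiction but would leave a pre-declared special-interest event untabulated by group for about half of follow-up.

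**Conclusion.** The point holds. Section 9.9 and the TEAE rules in Sections 7 and 9.9.6 conflict. Following Section 9.9.6 leaves dated adverse events with onset on Study Days 32 to 60 out of every AE incidence table: 29 of 60 days, or 26 to 32 days depending on when the last call falls.

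That is a share of days, not of events. The share of events could be about 4%, 17% or 48% under the onset patterns assumed above, and the SAP offers no basis for choosing among them.

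This should be fixed before the tables are produced. It concerns the completeness and consistency of the safety tables; no hypothesis test or primary pharmacokinetic result changes.

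**What to change.** 1. Reconcile Sections 7, 9.9 and 9.9.6 so that they agree on the period over which adverse events are summarized.
2. Keep the 30-day TEAE tables if wanted. Add to Section 9.9.6 summary tables on the safety analysis set, by treatment group, system organ class and preferred term, for all adverse events with onset or worsening from the start of study drug through the Day 60 contact (Study Day 57 to 63). At a minimum, cover serious, special-interest and fatal events.
3. State in Section 9.9.6 which window each AE table uses.
4. State whether the overview death row is limited to TEAEs.

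The cost is SAP wording plus about three or four tables on the existing 14.3-5.1.2 template, from data already collected. The small downside is that some unrelated late events will enter the added counts.
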